2.2.3 Entomological secondary endpoints and analysis

The tests used will depend on the type of data collected (e.g., survivorship of blood fed mosquitoes in each arm per collection interval, proportion of mosquitoes parous/arm per collection interval, etc...) The following are key secondary entomological outcomes.

- Human biting rate (HBR). This is defined as the number of mosquitoes captured per person per time period. For aspirated, indoor resting, blood fed mosquitoes, the HBR is calculated by dividing the house or household catch by the number of humans living in that house or household. For host-seeking mosquitoes caught in light traps placed next to individual persons sleeping in tents (outdoors) or under bednets (indoors), the HBR is simply the catch number per 1 person.
 - This will be compared between intervention and control arms and further analyzed by mosquito species (*An. gambiae* s.l [or *An. gambiae* s.s., *An. coluzzi*, *An. arabiensis*]; *An. funestus*)
 - Indoor blood fed HBR
 - Indoor host-seeking HBR
 - Outdoor host-seeking HBR
 - Total HBR
- Sporozoite rate. A representative proportion of mosquitoes captured per time period and per mosquito species will be tested for prevalence of infection with *Plasmodium* sporozoites by genetic testing of their heads+thoracies.
 - This will be compared between intervention and control arms and analyzed in total.
 - o This will also be analyzed by identified *Plasmodium* species: *P. falciparum*, *P. ovale*, *P. malariae*, or *P. vivax*.
- Changes in participants' antibody responses to Anopheles saliva protein(s).
 Antibodies will be eluted from filter paper samples containing a representative proportion of participants' capillary finger-prick blood that were collected at the beginning and end of each intervention season. Paired sets antibodies from individual participants (beginning and end of season collections) will then be tested for binding to Anopheles saliva protein(s), the binding change per person calculated, and then these data compared between participants from the intervention and control arms.
- The survival rate of blood fed mosquitoes. These blood fed mosquitoes were collected per time period, brought back to the field insectary and held for 3 days to measure their survivorship over that time. Survivorship will be compared between intervention and control arms and analyzed by time period captured, by mosquito species, and by location in clusters where they were captured.

These data (except for survival rate, see below) will also be used to make generalized linear and non-linear mixed effects models in R and SAS to understand the functional relationships of measured entomological and parasitological variables and the relative

contributions of various independent variables on variation in the dependent variable. Final model choices will be indicated by the distribution of the dependent variable as well as assessments for the need to model an additional parameter to account for variability in the data (e.g., Poisson vs Negative Binomial). The survival rate of blood fed mosquitoes will be analyzed using a log-rank test and visualized using a Kaplan Meier curve.

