### 3.2.2. Secondary

- AE monitoring will occur both actively and passively. All AE will be graded and analyzed by seriousness, intensity and causality. AE monitoring in this study is crucial to properly weigh the potential benefits vs. potential risks of the study.
- In the entire enrolled populace, passive monitoring of AEs will occur through spontaneous reporting of events to the study clinical team, and recorded on CRFs. AEs will be recorded from the entire enrolled populace, regardless if they were treated with ivermectin/placebo or not eligible to take the intervention. AEs will also be actively monitored on the days of distribution of ivermectin/placebo through direct questioning of AEs and recording on CRFs by study nurses for all participants. AE will be recorded over the intervention period occurring during the 1st and 2nd rainy seasons. More specifically, AEs will be recorded from the start of the first MDA of each rainy season to 1 month after the last MDA of that season.
- For those children enrolled in the active case detection cohort, where children are visited weekly to assess for malaria incidence, active monitoring of AEs will occur through direct questioning of AEs by the study team. Additionally, passive monitoring of AEs will occur by

---

participants spontaneously reporting directly to the nurses when the nurses are in the villages performing active case detection of malaria in the child cohort, or spontaneously reporting indirectly to the nurses via communication through the village community health worker (who will then communicate the AE directly to the nurse or field physician).

- For women that become pregnant during the intervention period, monitoring for birth outcomes will be conducted. Pregnancies will be followed in both arms of the study.
- Entomological indices will provide a first-order mechanistic explanation of the intervention's effect on malaria incidence (the primary outcome): Wild, blood-fed, indoor-aspirated, *Anopheles* will be held in cages and scored for survival rates over time, which will be analyzed across arms. The age structure of captured *Anopheles* will be analyzed over time and analyzed across arms. Captured wild mosquitoes will be dissected and analyzed for sporozoite infection rates over time and analyzed across arms. A cohort of participants' sera immuno-reactivity to an *Anopheles* saliva antigen will be analyzed over the intervention period of each season.

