## 10. STATISTICAL CONSIDERATIONS

### 10.1. Study Hypotheses

The primary objective hypothesis is that repeated IVM MDAs (the intervention) coinciding with SMC rounds and other standard-of-care malaria control measures (LLIN distribution, IPTp) will significantly reduce the incidence of childhood malaria compared to the placebo intervention. This hypothesis will be tested in a 2-arm superiority trial with a cluster randomized design. The primary outcome measures of incidence of malaria episodes among village children ≤ 10 years of age in each arm will be used to test the hypothesis. The primary objective null hypothesis is that that repeated IVM MDAs coinciding with SMC rounds and other standard-of-care malaria control measures will have no effect on the incidence of childhood malaria compared to placebo MDAs coinciding with SMC rounds and other standard-of-care malaria control measures.

Secondary objective hypotheses:

- The risk of adverse events (AEs) per participant in the intervention arm occurring over the intervention phase of the trial will not differ relative to the risk of adverse events in the control arm.  
*Null: The risk of adverse events (AEs) per participant in the intervention arm occurring over the intervention phase of the trial will not differ relative to the risk of adverse events in the control arm.*
- The survival rates of wild blood fed *Anopheles gambiae* s.l. will be significantly reduced, and age-structure and entomological inoculation rate in wild *Anopheles gambiae* s.l. significantly younger/lower, in those captured from intervention arm villages as compared to those captured control arm villages at equivalent time intervals during the intervention phase. Also, the immuno-reactivity of intervention-arm participants' IgG over time to an *Anopheles* salivary gland peptide will be significantly lower than that from control arm participants.  
*Null: The survival rates of wild blood fed Anopheles gambiae s.l., and parity and sporozoite rates in wild Anopheles gambiae s.l., will not differ in those captured from intervention arm villages as compared to those captured control arm villages at equivalent time intervals during the intervention phase. Similarly, the immuno-reactivity of intervention-arm participants' IgG over time to an Anopheles salivary gland peptide will be no different than that from control arm participants.*

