#### 10.4. **Final Analysis Plan**

The final statistical plan will be written in detail in the finalized standard operating procedure, before the start of the intervention phase, to ensure that the sampling plan (e.g. number of nurse visits, number of mosquitoes and blood samples) collected are appropriate for the intended analyses. In general, standard, two-tailed statistical hypothesis testing  $\alpha=0.05$ , as well as estimating and comparing the effect sizes and confidence intervals, will be used to measure the differences in entomological and parasitological secondary outcomes between arms. The tests used will depend on the type of data collected (e.g., survivorship of blood fed mosquitoes in each arm per collection interval, proportion of mosquitoes parous/arm per collection interval, average counts of trophozoites/slide or counts of the parasite molecular force of infection, sporozoite rates in mosquitoes), and their distributions. These data will also be used to make generalized linear and non-linear mixed effects models in R, SAS or other programs to understand the functional relationships of measured entomological and parasitological variables and the relative contributions of various independent variables on variation in the dependent variable.

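### The mosquito-saliva antibody endpoint is compared between arms as a raw change score, without adjusting for the start value already collected and without a village term.

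*SAP*

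**What the plan says.** Protocol 3.2.2 lists, among the entomological secondary outcomes, a cohort of participants' "sera immuno-reactivity to an" Anopheles saliva antigen, followed over the intervention period of each season. Protocol 10.1 states the hypothesis: IgG reactivity over time in the intervention arm to the "salivary gland peptide will be significantly lower than that from control arm participants". Protocol 10.4 plans "standard, two-tailed statistical hypothesis testing" at alpha 0.05 for entomological outcomes generally.

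SAP 2.2.3 gives the analysis. Antibodies are eluted from "capillary finger-prick blood that were collected at the beginning and end of each intervention season", paired within person. The SAP then has "the binding change per person calculated, and then these data compared between participants from the intervention and control arms".

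Two other sentences in SAP 2.2.3 bear on this. The section opens by saying "The tests used will depend on the type of data collected". It closes with "These data (except for survival rate, see below) will also be used to make generalized linear and non-linear mixed effects models", whose stated purpose is to "understand the functional relationships of measured entomological and parasitological variables". Neither sentence names a baseline covariate, a village term or a rule for combining seasons in the arm comparison of this endpoint. By contrast, SAP 2.2.2 says that the parasitological endpoints will follow the approach of the primary analysis, with adjusted models.

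**The concern.** A change score forces the coefficient of the start value to be exactly 1. Unless the regression slope of end on start really is 1, this adds noise that a fitted slope would remove. It also over-corrects a chance difference at the start. Chance differences are a practical worry here: 14 villages are allocated by drawing envelopes, and Protocol 5.3.1 describes no stratification.

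The comparison is described between participants, while randomisation was by village. A test that treats participants as independent would ignore the clustering that the primary model takes care to include.

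Season 2 raises a different question. SAP 1.3 starts season 2 at MDA #5, so the season-2 start sample is taken after MDA rounds 1 to 4. It is a post-treatment measurement, and subtracting it also subtracts whatever arm difference is present at that time.

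At stake is the precision of one secondary endpoint and the meaning of its season-2 estimate. The primary endpoint is not affected.

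**Working it through.** **No figure to reproduce.** The documents give no sample size, SD, correlation or effect size for this endpoint. Everything numerical below rests on assumed values.

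**Precision, independent individuals.** Let the end-value SD be s, the start-value SD be k·s, and the start-end correlation be rho.

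- Change-score variance: s²(1 + k² − 2·rho·k).
- Covariate-adjusted variance (large sample): s²(1 − rho²).
- Change-score variance minus adjusted variance: s²(k − rho)², which is never negative. Adjustment is therefore at least as precise, with equality when k = rho.

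With equal variances (k = 1) the ratio of adjusted to change-score variance becomes (1 − rho²)/(2(1 − rho)) = (1 + rho)/2:

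| rho (assumed) | Variance ratio | Extra people the change score needs | Power of change score if adjusted analysis has 80% |
|---|---|---|---|
| 0.3 | 0.65 | 1/0.65 − 1 = 54% | 62% |
| 0.5 | 0.75 | 1/0.75 − 1 = 33% | 68% |
| 0.7 | 0.85 | 1/0.85 − 1 = 18% | 73% |
| 0.8 | 0.90 | 1/0.90 − 1 = 11% | 76% |

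The power column uses two-sided alpha 0.05: the non-centrality 1.96 + 0.84 is multiplied by the square root of the ratio.

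**Unequal variances.** At rho = 0.5 and k = 0.6 (assumed), the ratio is 0.75/(1 + 0.36 − 0.60) = 0.75/0.76 = 0.99. The gain is about 1%, not 25%.

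**Fourteen villages.** A simulation of village means used 7 villages per arm, 4,000 runs, assumed ICC 0.05, assumed 50 people per village, and the same rho within and between villages. The ratio of adjusted to change-score variance was 0.73, 0.84, 0.94, 0.99 and 1.03 at rho 0.3, 0.5, 0.7, 0.8 and 0.9. The gain shrinks as village means become more correlated. At rho 0.9 it turns into a slight loss, because estimating a slope from 14 points has a cost.

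**Chance imbalance.** With equal variances, if the arms differ by d at the start of season 1, the expected end difference due to that imbalance is rho·d. The change score leaves rho·d − d = −(1 − rho)d; the adjusted estimate leaves nothing on average. Over repeated randomisations d averages zero, so the change score is unbiased.

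**Season 2.** Let D be the arm effect at the end of season 2 and f·D the arm difference already present at its start (equal variances):

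- Change score estimates (1 − f)D.
- Adjusting for the season-2 start value estimates (1 − rho·f)D.
- Adjusting for the pre-season-1 value estimates D.

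With f = 0.25 and rho = 0.5 these are 0.75D, 0.875D and D. With f = 0 all three equal D. The documents do not give f. Adjusting for the season-2 start value therefore reduces the subtraction but does not remove it.

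**The case against.** The strongest reply is that the within-season change may be what the investigators want. The SAP labels the endpoint as a change in antibody response, and Protocol 3.2.2 frames it season by season. An end-of-season-2 value adjusted for a pre-season-1 value asks a cumulative two-season question. This stands in part: the two quantities differ, and the change score deserves to be reported. But the hypothesis in Protocol 10.1 is about lower reactivity over time, which a smaller within-season rise in season 2 does not by itself establish.

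A second reply is that adjustment is not excluded, since tests are left to data type and mixed models are foreseen. That is right, and a reader should not infer that the plan rules adjustment out. However, those models are additional and aimed at relationships among variables; the arm comparison itself is left unadjusted.

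Three stronger readings are not supported:

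- **Season 2 is biased toward no effect.** SAP 2.3.3 puts mosquito killing at 2 to 3 weeks per MDA. Follow-up ends about November (Protocol 7.5) and MDA resumes in July, roughly eight months later. No antibody persistence is given, so carry-over is possible but not shown.
- **This is the trial's only direct measure of bite exposure.** SAP 2.2.3 also measures human biting rate indoors and outdoors, and Protocol 7.10.1.2 plans DNA matching of blood meals to people.
- **A gain of 15% to 35% can be expected.** Those figures need equal variances and independent individuals. Transmission is highly seasonal (Protocol 2.2), so equal variance at the start and end of a season cannot be taken for granted.

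**Conclusion.** The point holds as a low-cost improvement to a secondary analysis. The SAP's stated arm comparison is an unadjusted per-person change with no village term, although the start value is collected. Adjusting for that value is at least as precise in large samples and corrects chance imbalance.

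In season 1 this is a matter of precision, not validity. The variance reduction runs from 35% (rho 0.3) to 15% (rho 0.7) under equal variances and independent individuals. It can be close to nil if the start and end SDs differ or village means are strongly correlated. Neither rho nor the SDs are in the documents, so no single figure can be claimed.

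In season 2 it is certain that the start sample is post-treatment. Whether that costs anything depends on an arm difference persisting to that sample, which the documents do not establish.

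**What to change.** State in SAP 2.2.3 that the main arm comparison is a mixed model of end-of-season binding on arm and start-of-season value. It should include a village random effect and the Kenward-Roger correction already used for the primary model (SAP 2.1.3). Report each season separately.

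For season 2, use the pre-season-1 value as the covariate where that sample exists. The blood-sampling table in Protocol section 4 schedules before-season filter papers for the child cohort and the transect households. SAP 2.2.2 states whole-cohort filter papers for 2020 only, and newborns and new residents join later, so some participants will lack this value. For them, report the result adjusted for the season-2 start value, labelled as conditional on a post-treatment measurement. Do not fill the gap with a village mean, which would mix individual-level and village-level adjustment.

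Keep the change score as a descriptive or sensitivity result, since the within-season change is of interest in itself.

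The cost is a few sentences in the SAP, slightly more analysis work, and possibly assaying some stored season-1 samples for participants measured in season 2. No new blood collection is needed.

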**Table 3: Summary of the study groups and schedule for blood sampling.**

Group	Number to sample	Ages	What and when samples collected				
			BS=blood smear FP=filter paper	BS&FP -when malaria diagnosed	BS&FP -before season	BS&FP -between the second and third MDA each season	BS&FP -dry season/ post intervention (only from select participants)
Child cohort (followed with active case surveillance)	~1800	≤10 yr. olds	BS&FP -when malaria diagnosed	BS&FP -before season	BS&FP -between the second and third MDA each season	BS&FP -post season	BS&FP -dry season/ post intervention (only from select participants)
Households# on village transects (3 villages/arm; ~8 households/village)	~380	all note: ≤10 yr. olds will be sampled in the ACD cohort		BS&FP -before season	BS&FP -between the second and third MDA each season	BS&FP -post season	BS&FP -dry season/ post intervention
PK-PD modeling cohort	180	5-10yo (n=30 per arm) 11-18yo (n=30 per arm) ≥19yo (n=30 per arm)	Each participant sampled for capillary blood up to 5 of the following time points after their last dose of IVM: 0h (pre-last dose), 1h, 4h*, 8h, 12h*, 24h, 48h, 52h, 60h, 72h, 7d*, 14d, 21d and 28d. *venous blood will be collected simultaneously at these time points				

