## 5.3. Treatment Assignment Procedures

### 5.3.1. Randomization Procedures

This will be a cluster (village)-randomized trial. Once the chiefs/leaders and heads-of-households of all fourteen selected villages give their verbal consent to participate following informational and question and answer meetings with the study team, a village representative and the CHWs representing each village will be asked to participate in a public randomization event at the facilities of the district health authority, attended by the district medical director and members of the study team. In front of the attendees, the numbers “1” and “2” will be written on 7 cards each, which will be sealed in identical opaque envelopes, mixed in a container, and then randomly pulled from the container by each village representative. Villages will be assigned to the arm written on the card selected by this representative, and the procedures will be video recorded. These arm designations will be linked to the masked active ingredient tablet or placebo (below).

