2. ANALYSIS PLAN

2.1 Primary analysis

The primary outcome will be analyzed as intention-to-treat (ITT). The number of episodes per week among the active case detection (ACD) cohort (children age ≤ 10 years) will be used as the primary measurable outcome to evaluate the impact of the intervention when compared to the control arm. The active case detection cohort includes all enrolled children regardless of

eligibility or receipt of MDA or SMC. A mixed effects regression analysis with Poisson distribution will be used to assess the impact. The primary analysis will include a random effect for cluster (village), and 3 fixed effects (treatment effect, year, and sex; all binary covariates, no interactions evaluated). Subgroup analyses will include an evaluation of fixed effects such as LLIN use, age, and treatment with SMC or IVM. Estimates for the intervention effect from the primary analysis as well as subgroup analyses will be reported along with 95% confidence intervals. The statistical program SAS v9.4 (SAS Institute Inc., Cary, NC) will be used for primary statistical analyses. Secondary data generated from Aim 1 will include adverse events (AE), severe adverse events (SAE), and their relationship to the intervention/placebo. The risk of SAE and AE will be compared between intervention and control arms by calculating risks ratios and attributable risks with 95% confidence intervals.

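### SAP 2.2.3 compares mosquito survival between arms with a log-rank test alone, making no allowance for clustering by village and departing from protocol 10.4 (secondary endpoint, should be fixed)

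*SAP*

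**What the plan says.** Allocation is by village (protocol 5.3.1): "This will be a cluster (village)-randomized trial". Reduced survival of wild blood-fed mosquitoes in the intervention villages is a stated secondary hypothesis (protocol 10.1). For entomological outcomes, protocol 10.4 plans "standard, two-tailed statistical hypothesis testing" at alpha 0.05.

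Under SAP 2.2.3, mosquitoes are "brought back to the field insectary and held for 3 days to measure their survivorship over that time". Survivorship is compared between arms and "analyzed by time period captured, by mosquito species, and by location in clusters where they were captured". On method, the SAP first says of the entomological data: "These data (except for survival rate, see below) will also be used to make generalized linear and non-linear mixed effects models". It then gives the method for survival: "The survival rate of blood fed mosquitoes will be analyzed using a log-rank test and visualized using a Kaplan Meier curve". No village or house effect, robust variance or cluster-level summary is named.

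Elsewhere the plan does handle clustering. The primary model has a village random effect and a Kenward-Roger correction for the small number of clusters (SAP 2.1, 2.1.3), and the parasitological endpoints follow that approach (SAP 2.2.2). Protocol 10.4 gives mosquito survivorship as an example of the entomological data and says that these data will also go into mixed-effects models.

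**The concern.** A standard log-rank test treats each mosquito as an independent unit. Mosquitoes caught in one village, and more so in one house or one collection, share conditions that may affect survival whatever the arm. Since the arm is fixed for a whole village, variation between villages goes straight into the arm difference, and the log-rank variance does not include it. The P value is then too small, as is the uncertainty attached to the survival difference.

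What is at stake is the reading of mechanism. The protocol presents the entomological indices together as the first-order explanation of any effect on malaria, and mosquito survival is one of them. A falsely small P value could be taken as confirming the mechanism, or as an effect in the wrong direction.

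**Working it through.** **Figure to reproduce.** None: the documents give no sample size, power or event count for mosquito survival.

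**Inputs from the documents.** Village randomisation, 7 villages per arm (protocol 5.3.1); two-sided alpha 0.05 (protocol 10.4); 3 days of holding (SAP 2.2.3).

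**Assumed inputs.** Mosquitoes per village (*m*), three-day mortality and between-village variation. The coefficients 0.258 (SAP 1.3) and 0.2 (protocol 10.2) describe malaria rates and serve below only as illustrative values for the mosquito death hazard.

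**Step 1, analytic.** Take 80% three-day survival and a between-village SD of *s* on the logit scale.

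- ICC ≈ *s*² × 0.8 × 0.2 = 0.16*s*²
- Design effect DE = 1 + (*m* − 1) × ICC
- Actual type I error of a nominal 5% test = 2[1 − Φ(1.96/√DE)]

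| *m* | *s* | ICC | DE | Type I error |
|---|---|---|---|---|
| 40 | 0.1 | 0.0016 | 1.06 | 0.057 |
| 40 | 0.2 | 0.0064 | 1.25 | 0.080 |
| 100 | 0.1 | 0.0016 | 1.16 | 0.069 |
| 100 | 0.2 | 0.0064 | 1.63 | 0.125 |
| 100 | 0.4 | 0.0256 | 3.53 | 0.297 |
| 300 | 0.2 | 0.0064 | 2.91 | 0.251 |
| 300 | 0.4 | 0.0256 | 8.65 | 0.505 |

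A null simulation (4,000 trials per setting, 3 v 3 villages) with a pooled two-sample test of three-day survival as a proxy agrees. It gave 0.123 and 0.305 at *m* = 100 (*s* = 0.2, 0.4) and 0.248 and 0.496 at *m* = 300. A t-test on the six village proportions gave 0.048-0.051.

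**Step 2, an actual log-rank test.** Null simulation, 20,000 trials per cell, deaths counted on three days, gamma-distributed village frailty on the death hazard. Type I error at 30% three-day mortality, shown as 3 / 7 villages per arm:

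| Mosquitoes per village | CV 0 | CV 0.1 | CV 0.2 | CV 0.258 |
|---|---|---|---|---|
| 40 | 0.049 / 0.051 | 0.062 / 0.063 | 0.105 / 0.105 | 0.136 / 0.139 |
| 100 | 0.052 / 0.047 | 0.086 / 0.086 | 0.185 / 0.188 | 0.251 / 0.253 |
| 200 | 0.049 / 0.048 | 0.117 / 0.122 | 0.283 / 0.280 | 0.372 / 0.378 |

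Over mortality of 15-50%, the cells with village variation range from 0.055 to 0.471. The test is valid only when villages do not vary. More villages per arm do not cure the inflation, because it depends on mosquitoes per village and the ICC. A t-test on village survival proportions (df 4 or 12) stayed at 0.045-0.052 in every cell.

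**Step 3, how many villages supply mosquitoes.** Not stated. The protocol summary mentions entomological sampling transects, and protocol Table 3 gives "3 villages/arm; ~8 households/village" for transect households, but that row schedules blood sampling. Protocol section 4 says only that mosquitoes are captured from intervention and control clusters. If it is 3 v 3, there are C(6,3) = 20 possible allocations, so an exact two-sided village permutation test cannot go below 2/20 = 0.10. With 7 v 7 the floor is 2/3432.

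**The case against.** The strongest reply is that this is one of several secondary, explanatory endpoints, that no trial decision is tied to it, and that the size of the error rests wholly on assumed inputs. All of that stands. With few mosquitoes per village and little variation the error is only about 6%, and the 50% figure needs 300 per village and SD 0.4 together.

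It can also be said that the SAP does not use the word unstratified, and that its breakdowns leave stratification by period or species open. That is fair, but neither stratification nor a breakdown by location brings variation between villages into the variance of the arm comparison.

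Four stronger readings are tempting, and the documents do not support them:

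- *Village variation will often look like a highly significant drug effect.* At P < 0.001, replacing 1.96 by 3.29 in the formula gives about 1-8% with 100 per village and 5-26% with 300 (SD 0.2-0.4).
- *Every other entomological endpoint has a clustered arm comparison.* SAP 2.2.3 says only that the other data will also enter mixed models, to study functional relationships; it specifies no village effect there.
- *Only 3 villages per arm supply mosquitoes.* This is plausible, but it is carried over from a blood-sampling row. The floor of 0.10 applies only in that case.
- *Clustering of mosquito survival was never considered.* Protocol 10.4 includes survivorship in the mixed-model work; it is the SAP that removes it.

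**Conclusion.** The point holds as a should-fix on a secondary endpoint. The only test named for mosquito survival ignores the unit of randomisation, and the SAP is narrower than protocol 10.4 without giving a reason. The direction is certain if survival varies between villages at all: too many false positives and understated uncertainty. The size is not known. On the assumptions in the working it runs from about 6% to 50% against a nominal 5%, with about 19% in a middle case (hazard CV 0.2, 30% mortality, 100 mosquitoes per village). A reader should not infer that the trial's main conclusion is at risk, because the primary malaria analysis models village and corrects for few clusters.

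**What to change.** In SAP 2.2.3, replace the log-rank test as the arm comparison.

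- **Main analysis:** a village-level comparison of three-day survival, for example a t-test on village proportions with df equal to the number of contributing villages minus 2.
- **Alternative, if enough villages contribute:** a discrete-time or Cox model with a village random effect, house or collection effects where they can be estimated, and small-sample df based on villages. With about six villages, nested random effects would be weakly estimated, so the village-level comparison is safer.
- **Reporting:** keep Kaplan-Meier curves as description only, and give the number of villages and mosquitoes behind each comparison.
- **Consistency:** reconcile SAP 2.2.3 with protocol 10.4. The same edit could state how village enters the arm comparisons of the other entomological indices.

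The cost is SAP wording and standard software, with no new data if village, house and collection date are recorded for each mosquito. The price is wider intervals for this endpoint.
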